4.1. Overall Design

This is a Phase 2, proof-of-concept, placebo-controlled, double-blind, randomized study in adult participants with moderately to severely active RA who have had an inadequate response to csDMARDs, or to bDMARDs/tsDMARDs. Participants will be administered LY3462817 or placebo IV Q4W.

Screening Period (Visit 1, Days -42 to -1)

Participants will sign the informed consent document(s) at Visit 1, prior to completion of any procedures. Participants will be evaluated for study eligibility \leq 42 days prior to the baseline visit (Visit 2).

Period 1: Double-blind Treatment (Visits 2 to 6; 12 weeks)

At the baseline visit (Visit 2), participants who fulfill the eligibility criteria will be randomized to receive LY3462817 700 mg, LY3462817 300 mg, or placebo in an allocation ratio of 2:1:1.

The double-blind treatment period will establish the clinical efficacy and safety of LY3462817. The study will be evaluated for the primary objective at the end of the double-blind treatment period.

Period 2 (Visits 6 to 10; 12 weeks)

Data from a Study KDAC interim analysis that includes Week 12 data from participants in the KDAC 700-mg cohort, must be reviewed prior to a participant proceeding to Period 2 in Study KDAD.

At Week 14, participants will be evaluated for clinical benefit.

Participants assigned to LY3462817 at baseline, and achieving low disease activity (CDAI \leq 10) at Week 14 will continue to receive LY3462817 at the randomized dose through Week 24 to assess safety and tolerability and evaluate efficacy.

All other participants at Week 14, regardless of baseline treatment assignment, will stop study drug infusions and should receive standard of care treatment at the investigator's discretion.

Posttreatment Safety Follow-up Period (Visits V801 and 802; 12 weeks)

Following Period 2, participants will be followed posttreatment for 12 weeks to assess safety, study drug exposure, and clinical disease activity measures. Participants who discontinue the study intervention per Section 7 will have their last visit at 12 weeks from the last administration of the study intervention.

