At the baseline visit (Visit 2), participants who fulfill the eligibility criteria will be randomized to receive LY3462817 700 mg, LY3462817 300 mg, or placebo in an allocation ratio of 2:1:1.

The double-blind treatment period will establish the clinical efficacy and safety of LY3462817. The study will be evaluated for the primary objective at the end of the double-blind treatment period.

Period 2 (Visits 6 to 10; 12 weeks)

In Period 2, participants assigned to LY3462817 at baseline, and achieving low disease activity (CDAI ≤ 10) at Week 14 will continue to receive LY3462817 to assess safety and tolerability data and evaluate clinical activity with additional dosing. All other participants at Week 14, regardless of baseline treatment assignment, will receive standard of care treatment at the investigator's discretion.

Post-treatment Safety Follow-up Period (Visits V801 and 802; 12 weeks)

Following Period 2, participants will be followed posttreatment for 12 weeks to assess safety, study drug exposure, and clinical disease activity.

Disclosure Statement: This is a parallel, 3-arm treatment study that is participant-blinded and investigator-blinded.

Number of Participants:

[figure not shown]
Approximately 80 participants will be randomly assigned to study intervention. At the completion of the study, approximately 40 participants will have been randomized to LY3462817 700 mg and 20 participants will have been randomized to LY3462817 300 mg and placebo during the double-blind treatment.

Intervention Groups and Duration:

Participants will receive 1 of the following study interventions: intravenous LY3462817 300 mg, 700 mg, or placebo every 4 weeks for 12 weeks. Participants assigned to LY3462817 at baseline, and achieving low disease activity (CDAI ≤ 10) at Week 14 will continue to receive LY3462817 through Week 24.

Data Monitoring Committee: No data monitoring committee, but there will be an internal assessment committee.

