6.3. Measures to Minimize Bias: Randomization and Blinding

To preserve the blinding of the study, a minimum number of Lilly personnel who are not directly involved with investigational sites will see the randomization table and treatment assignments before the study is complete.

Joint, disease activity, and safety assessments

Joint Assessor

To prevent potential bias due to observed efficacy or laboratory changes, a “dual assessor” approach will be used to evaluate efficacy and safety. The Joint Assessor (or designee) should be a rheumatologist or skilled arthritis assessor. The Joint Assessor will be responsible for completing the joint counts. To ensure consistent joint evaluation throughout the trial, individual participants should be evaluated by the same Joint Assessor for all study visits. The Joint Assessor must not access or discuss with the participant the patient-reported assessments, Physician’s Global Assessment of Disease Activity (PhGADA_VAS), and safety assessments.

Safety Assessor

The Safety Assessor (or designee) should be a rheumatologist (or medically qualified physician) and will have access to both safety and efficacy data. The Safety Assessor may be the principal investigator. The Safety Assessor will be responsible for completing the PhGADA_VAS. To ensure consistent PhGADA_VAS throughout the trial, the instrument should be evaluated by the same physician at all study visits. The Safety Assessor will have access to source documents, laboratory results, and electronic case report forms (eCRFs) and will be responsible for making treatment decisions based on a participant’s clinical response and laboratory parameters.

Method of treatment assignment

Assignment to treatment groups will be determined by a computer-generated random sequence using an interactive web-response system (IWRS).

Participants will be stratified by prior use of csDMARD only or by tsDMARD/bDMARDs use (yes versus no).

Emergency unblinding

In case of an emergency, the investigator has the sole responsibility for determining if unblinding of a participant's treatment assignment is warranted. Participant safety must always be the first consideration in making such a determination. If a participant's treatment assignment is unblinded, the sponsor must be notified immediately.

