6.5.2. Prohibited Concomitant Therapy

Live vaccinations are not allowed up to 3 months prior to screening or at any time during the study. Live herpes zoster vaccination is not permitted within 30 days of planned randomization or at any time during the study.

Nonlive seasonal vaccinations and/or emergency vaccination, such as rabies or tetanus vaccinations, are allowed.

6.5.3. Standard of Care Therapy after Week 14

All placebo patients should begin SOC therapy at Week 14 at the investigator's discretion.

Participants randomized to LY3462817 at baseline and not achieving low disease activity (CDAI ≤ 10) at Week 14 will no longer receive study drug infusions and should receive SOC therapy at the investigator's discretion.

Participants who achieve low disease activity at Week 14, and maintain treatment with LY3462817 during Period 2, can be switched to SOC prior to Week 24 if the participant stops receiving clinical benefit. Name(s) and dosage regimen(s) must be recorded for the SOC therapy. Standard of care medications will not be supplied by the sponsor.

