8.1.10. Clinical Disease Activity Index (CDAI)

The CDAI is similar to the SDAI, but it allows for immediate scoring because it does not use a laboratory result. The CDAI is calculated by adding together scores from the following assessments:

- number of swollen joints (0 to 28)
- number of tender joints (0 to 28)
- PaGADA_VAS (0 to 100 mm), and
- PhGADA_VAS (0 to 100 mm) (Aletaha and Smolen 2005).

Remission is defined as a CDAI score of ≤ 2.8 (Felson et al. 2011). Low disease activity is defined as a CDAI score of ≤ 10 .

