9.5. Interim Analyses

Analyses for the primary database lock will be conducted as described in Section 9.4 when all participants have completed the double-blind treatment period or discontinued treatment.

One interim analysis of the safety and efficacy data will be planned prior to database lock, to support planning activities. This will be done when approximately 40% to 60% of participants have completed Period 1 (double-blind treatment) or have discontinued treatment. Bayesian posterior probabilities will be calculated to assess the efficacy of LY3462817 700 mg versus placebo for DAS28-CRP for Period 1 at the interim analysis. The decision rules based upon the posterior probability results will help in deciding whether to support further clinical development of LY3462817. Additionally, this interim analysis will aid in the development of PK/PD modeling.

Other interim analyses may be conducted as needed. All interim analyses will be used to support planning activities associated with the clinical development program and to aid in the development of PK/PD modeling. Since the study may terminate early only for safety and/or futility, no adjustment of type I error will be performed. Information about interim futility and decision rules will be provided in the SAP.

Internal assessment committee

Assessment of unblinded interim data will be conducted by an internal assessment committee (AC) with a limited number of prespecified members who do not have direct site contact or data entry or validation responsibilities (see Section 10.1.5, Appendix 1). Unblinding details will be specified in the unblinding plan section of the SAP or in a separate unblinding document. Information that may unblind the study during the analyses will not be reported to study sites or blinded study team until the study has been unblinded. Study sites will receive information about interim results only if they need to know for the safety of their participants.

Evaluation of unblinded safety data by the internal AC will occur if any of the following events are observed following review by the blinded safety review team:

- three or more participants experience TEAEs in the same system organ class, and these TEAEs assessed as severe by the investigator and are judged as related to blinded study treatment by the investigator.
- a malignancy SAE occurs during the study.

Pending the evaluation by the internal AC, enrollment and/or further dosing may be stopped.

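### At CDAI ≤10 the Week 14 rule shows the site who is on active drug and who is on placebo, but the blinding statement has no end point and the Joint Assessor is not shielded from the disposition

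*Protocol*

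**What the plan says.** **The rule.** Protocol Section 4.1 says of Week 14: "Participants assigned to LY3462817 at baseline, and achieving low disease activity" (CDAI ≤10) "will continue to receive LY3462817 at the randomized dose through Week 24". For the rest, "All other participants at Week 14, regardless of baseline treatment assignment, will stop study drug infusions". Section 6.5.3 adds: "All placebo patients should begin SOC therapy at Week 14 at the investigator's discretion". The synopsis and Section 4.2 agree. No masked placebo continuation is described.

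**Who knows the CDAI.** Section 8.1.10 says of the index that "it allows for immediate scoring because it does not use a laboratory result". Under Section 6.3 the Safety Assessor sees safety and efficacy data, scores PhGADA_VAS and makes treatment decisions.

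**Blinding.** The synopsis states: "This is a parallel, 3-arm treatment study that is participant-blinded and investigator-blinded". No end point is given, although only Period 1 is titled double-blind. The safety trigger in Section 9.5 counts severe events "judged as related to blinded study treatment by the investigator". Section 8 plans blinded safety review for the whole study.

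**Joint Assessor.** Section 6.3 says: "The Joint Assessor must not access or discuss with the participant the patient-reported assessments". The bar also covers PhGADA_VAS and safety assessments. Week 14 disposition, infusion status and start of standard of care (SOC) are not listed. The same person is meant to assess a participant at every visit, and the Schedule of Activities (SoA) runs joint counts to V802.

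**The concern.** Continuation depends on two things, assigned arm and CDAI, and the site knows the second. Once the disposition is known, the first can be read off for every participant at or below the threshold. The protocol does not acknowledge this. Its blinding statement is unqualified, its safety trigger still treats causality as blinded, and its one structural safeguard for joint counts omits the item that does the unmasking.

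At stake is how Period 2 is scored and reported. Joint counts, PhGADA_VAS and PaGADA_VAS after Week 14 feed the exploratory durability results (low disease activity or remission kept to Week 24), and every participant who continues is known to be on LY3462817. Relatedness of adverse events after Week 14 is the investigator's judgement and enters the safety tables. Without a change, these results could be reported as blinded when they are not.

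**Working it through.** The documents give no figure on this point, so the check enumerates the rule and then sizes it.

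**1. The rule by arm and CDAI** (Sections 4.1 and 6.5.3)

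| Assigned arm | CDAI at Week 14 | Disposition |
|---|---|---|
| LY3462817, either dose | ≤10 | continue, same dose |
| LY3462817, either dose | >10 | stop |
| Placebo | ≤10 | stop |
| Placebo | >10 | stop |

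With 2:1:1 allocation of about 80, there are 60 on LY3462817 and 20 on placebo, prior odds of 3:1.

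- CDAI ≤10: P(LY3462817 | continue) = 1 and P(placebo | stop) = 1.
- CDAI >10: everyone stops, so the disposition adds nothing.
- Continuers stay on their randomized dose, so 300 versus 700 mg is not revealed.

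**2. The Joint Assessor**, who is barred from two of the four CDAI components (PaGADA_VAS and PhGADA_VAS). Continue still gives P(LY3462817) = 1. For stop, with CDAI unknown and p the low-disease-activity rate on LY3462817:

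P(placebo | stop) = 0.25 / [0.25 + 0.75 × (1 − p)]

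- p = 0.10: 0.25 / 0.925 = 0.27
- p = 0.40: 0.25 / 0.70 = 0.36

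The prior is 0.25. Stopping therefore says little unless CDAI ≤10 is known or inferred, for example from low joint counts.

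**3. How many are unmasked.** Number = 60 × p(LY) + 20 × p(placebo). The rates are assumptions: 10–40% on LY3462817 and 5–20% on placebo.

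- Low: 60 × 0.10 + 20 × 0.05 = 6 + 1 = 7 of 80 (9%)
- High: 60 × 0.40 + 20 × 0.20 = 24 + 4 = 28 of 80 (35%)

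Whatever the rates, all continuers (6 to 24 here) are known to be on active drug.

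**4. What is scored afterwards.** The primary endpoint is at Week 12 (Visit 6), before the Week 14 decision (Visit 7). The first infusion governed by the decision is at Week 16. DAS28-CRP, DAS28-ESR and SDAI each include hsCRP or ESR, whose results are withheld from sites (Section 10.2); CDAI has no laboratory part. The open parts are joint counts and PaGADA_VAS in all four indices, and PhGADA_VAS in SDAI and CDAI.

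**5. Placebo at Week 24.** SAP Section 4.1 makes anyone who permanently stops study drug before the end of the treatment period a nonresponder, and defines that period as Periods 1 and 2 together. SAP Sections 4.5.1 to 4.5.4 and 4.5.7 also exclude observations after discontinuation. Every placebo participant stops at Week 14, so placebo response at Week 24 is fixed by rule, whoever counts the joints.

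**6. Conflicting descriptions.** The SoA dosing note makes Weeks 16–24 dosing depend on low disease activity alone; read literally, continuing would then reveal nothing. SAP Section 1.2 has all participants on LY3462817 in Period 2. Neither matches Section 4.1.

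**The case against.** The strongest reply is that nothing important was promised or lost. Only Period 1 is titled double-blind, Section 4.2 confines the placebo-controlled period to Period 1, the primary endpoint is already collected, and the durability objective is exploratory in a proof-of-concept study. Much of this stands, and it rules out several stronger readings that a reader might infer:

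- *That the protocol claims double-blind treatment throughout.* It does not. The synopsis statement is unqualified, which leaves Period 2 undefined.
- *That Week 12 results are biased.* They precede the decision.
- *That the durability set is exactly the unmasked set.* Durability starts from low disease activity or remission at Week 12 on four indices; unmasking turns on CDAI at Week 14. The sets overlap but differ.
- *That Week 24 response comparisons with placebo are distorted by scoring.* Placebo response is already fixed by nonresponder imputation.
- *That the Joint Assessor is fully unblinded.* This is so for continuers only; stopping alone is weak evidence.
- *That every participant learns the assignment.* Section 8.1.10 supports knowledge at the site; no passage says participants are told their CDAI.
- *That the committee's safety review is corrupted.* It reviews unblinded data, and the malignancy trigger does not use causality. Only the relatedness condition of the other trigger depends on the investigator's judgement.

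What survives is that the disposition does unmask a definable group, that Sections 8 and 9.5 still assume blinded safety data after it, and that the existing assessor bar omits it.

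**Conclusion.** The point holds at limited scope. For participants with CDAI ≤10 at Week 14, the disposition reveals active versus placebo to the site with certainty, and all continuers are known to be on LY3462817. Dose is not revealed and Week 12 endpoints are untouched. The exposed results are the joint-count, PhGADA_VAS and PaGADA_VAS parts of the exploratory Period 2 and durability results in continuers, and investigator causality after Week 14.

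The count of about 7 to 28 of 80 rests wholly on the assumed response rates. The logic does not, but it does take Sections 4.1 and 6.5.3 as the operative rule, which the SoA note and SAP Section 1.2 contradict. The documents give no basis for estimating the size of any resulting bias. The change is worth making because the blinding statement is inaccurate for part of the study and the correction costs very little.

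**What to change.** 1. **Protocol Section 6.3.** Add Week 14 disposition, infusion status and SOC start to what the Joint Assessor must not access or discuss, from Week 14 to V802. This protects joint counts only; PhGADA_VAS and PaGADA_VAS stay exposed. The small cost is that sites must keep infusion status out of the joint assessment.
2. **Synopsis and SAP.** Limit the blinding statement to Period 1 up to the Week 14 disposition. Have the SAP label Period 2 and follow-up efficacy and causality results as not blinded for participants with CDAI ≤10, and word the Section 9.5 trigger consistently. The cost is text only.
3. **Reconcile** the SoA dosing note and SAP Section 1.2 with Protocol Section 4.1, so that one description of Period 2 applies.

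A lock on adverse event causality before the disposition is released is not proposed. The documents do not describe how the disposition reaches the site, and Appendix 3 lets causality be revised as follow-up information arrives. None of these changes alters visits, sample size or staffing.

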4.2. Scientific Rationale for Study Design

Appropriateness of study population

Patients with RA are treated with the oral csDMARD methotrexate (MTX) as the first-line therapy either by itself or in combination with other therapies (Smolen et al. 2020). If the treatment target is not achieved with the initial csDMARD strategy, treatment modification often

involves use of bDMARDs, including tumor necrosis factor- α (TNF- α) inhibitors, or targeted synthetic tsDMARDs, in combination with csDMARDs (Smolen et al. 2020).

LY3462817 is being investigated to modulate the underlying immune dysregulation in the PD-1 pathway for the treatment of RA. Enrolling a mixed RA population who have had an inadequate response to csDMARDs, or to bDMARDs/tsDMARDs would allow patients with inadequate response to the current standard of care for RA across the disease spectrum to be included in the study.

Duration of treatment period and post-treatment follow-up

The placebo-controlled treatment period (Period 1) lasts 12 weeks. Participants randomized to LY3462817 at baseline can continue to receive treatment through Week 24 if achieving low disease activity by Week 14. Per current RA treatment guidelines (Smolen et al. 2020), therapy should be adjusted if no improvement is achieved by approximately ≤ 3 months within initiation, or if the target has not been reached by 6 months (Smolen et al. 2020). All participants randomized to placebo, and participants randomized to LY3462817 not achieving low disease activity by Week 14 should be switch to SOC RA therapy at the investigator's discretion. The length of the study placebo-controlled period falls within those guidelines.

The 12-week follow-up duration after 24 weeks of treatment is considered to be sufficient to evaluate safety and to explore the durability of biomarker and clinical disease activity changes achieved during the 24-week treatment period. Participants with disease activity that require any other treatment may discontinue the study at any time (Section 7.2).

Change from baseline in DAS28-CRP as the primary endpoint

The primary endpoint of this study is the change from baseline at Week 12 in the Disease Activity Score - C-reactive protein (DAS28-CRP) (Sections 3 and 8.1.1) and is a continuous measure that enables evaluation across multiple time points.

MRI

Magnetic resonance imaging (MRI) allows detailed assessment of the synovial joint. Magnetic resonance imaging features are frequently used as outcome measures in RA clinical trials. The Outcome Measures in Rheumatoid Arthritis Clinical Trials (OMERACT) RA MRI Scoring system (RAMRIS) outlines semiquantitative scoring of 5 RA pathologies: bone erosions, joint space narrowing, synovitis, tenosynovitis, and bone marrow edema in the wrist and metacarpophalangeal joints.

The primary interest in this study is to evaluate the effectiveness of LY3462817 in reducing inflammation in the joints. Enrolling study participants with active synovitis as determined by MRI will support overall evaluation of LY3462817 in reducing inflammation. Exploratory evaluation of a change in RAMRIS synovitis score at Week 12 will provide an objective measure of reduction in inflammation.

4.3. Justification for Dose

In this study, 2 dose levels of LY3462817 will be evaluated: 300 mg and 700 mg. These dose levels were selected based on preclinical pharmacology and toxicology data, and available clinical PK, target engagement, and safety data.

In Study KDAB, single LY3462817 IV doses of 350 and 700 mg have been evaluated in healthy subjects with no clinical significant safety concerns. The ongoing Study KDAC, is designed to evaluate multiple doses (4 total doses) of 75 mg, 300 mg, and 700 mg of LY3462817 IV Q4W in participants with psoriasis. The data from these studies and the plan to initiate KDAD is discussed in Section 2.2.

From available human PK and preclinical monkey toxicology data, the estimated margins of safety for 300 mg and 700 mg LY3462817 IV Q4W are ≥ 24 and >10-fold, respectively, based on both dose and steady-state exposure multiples.

The planned dose levels were also selected to evaluate an exposure range that is anticipated to be pharmacologically active. Receptor occupancy was used as a surrogate for pharmacological activity to help assess dose levels that saturate the target over the planned dosing interval. Doses of 350 mg and 700 mg have both been shown to saturate the receptor in plasma over 4 weeks and longer. However, significant uncertainties exist in translating RO profile in plasma to tissue with respect to drug concentration and receptor density (Chen et al. 2015; Rao et al. 2017). The 2 dose levels help account for these uncertainties, both of which directionally point to a decrease in extent and duration in tissue RO relative to plasma. Additionally, inclusion of 2 dose levels in KDAD will allow for a direct comparison with the corresponding dose levels in KDAC for assessing the impact, if any, of disease state on PK, RO, and sPD-1. If there is impact, having an additional dose level in KDAD will provide more data and confidence when projecting forward to a dose level or regimen ranging study.

